This proposal unites neuroimagers, experts in conducting and analyzing human PET studies with behavioral scientists, experts in developing and testing treatments for alcoholism. We will conduct the first-ever *in vivo* PET imaging study of KOR and NTX occupancy in two cohorts of HD (18 FHP and 18 FHN) and relate our imaging findings to FH and alterations of drinking behavior by NTX in the ADP. Through this work, we will advance our understanding of (a) the degree of involvement of the kappa system in reducing drinking in humans by NTX, (b) the contribution of FH to this relationship, and (c) refine the use of a new PET imaging tracer. In so doing, we will inform the development of future targeted pharmacotherapies for alcoholism and lay the groundwork for other important investigations into the KOR/dynorphin system *in vivo*.

Primary (P), Secondary (S), and Auxiliary (A) Specific Aims:

- P1. **Occupancy of KOR by NTX and drinking:** To determine the degree to which occupancy of KORs by a 100 mg/day dose of NTX mediates (influences the strength of) responsivity to NTX treatment in all heavy drinkers. It is expected that KOR occupancy will significantly mediate the relationship between NTX treatment and responsivity. „Responsivity“, measured via ADP, is the change in number of drinks consumed at the baseline ADP vs. NTX ADP.
- P2. **Family History of Alcoholism as a moderator:** To determine whether the relationship between NTX responsivity and occupancy of KOR is different in FHP vs. FHN heavy drinkers.
- P3. To determine if baseline KOR availability differs between heavy drinkers and healthy control socialdrinkers

S1. **Baseline KOR differences**

- a. To determine if baseline levels of KOR differ between FHP and FHN heavy drinkers.
- b. To determine if baseline KOR level is related to either baseline drinking or responsivity to NTX.

S2. **Identify and validate a reference region** (area devoid of specific binding) for our new KOR tracer. A reference region would simplify PET analysis.

S3. **Optimize the scan duration** for clinical populations being imaged with the new KOR tracer.

Shorter scans would increase compliance and decrease discomfort to subjects.

A1. **Relationship to other behavioral measures:** To determine if occupancy of KORs is related to measures of alcohol craving, stimulation or sedation, assessed in the ADP.

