- d. Dose, Timing of NTX and PK samples: We will taper subjects up to a NTX maintenance dose of 100 mg/day. 100 mg/day is the dose of NTX that has shown efficacy in many recent clinical trials [9], and our own preliminary evidence suggests that this dose may produce the greatest *reduction* in drinking in FHP drinkers but *increased* drinking in FHN drinkers. We considered testing more doses of NTX but we felt that this would not have been justified and would have been too costly. NTX dose will be administered at approximately 10 am each

day. All participants will start with 25 mg/day and be tapered up to 100 mg by day 3 of medication. We will obtain 2 blood samples for pharmacokinetic (PK) analysis during the post PET scan to confirm that steady state levels of NTX were in effect during these procedures. These PK samples will be tested for NTX and its major active metabolite, 6(beta)-naltrexol.

- e. Tobacco Use and Smoking breaks: In our experience, 50% of alcoholics who participate in our projects smoke cigarettes or use other tobacco products. In order to avoid nicotine withdrawal, on the ADP days, participants will be given smoke breaks until about an hour prior to the start of the ADP. We will not allow them to smoke during the ADP since this could not only alter their craving for alcohol but could also pose a potential risk (since YNHH is a nonsmoking facility and the participant would have to be walked out for a smoke break while intoxicated). On the PET days, we will allow regular smoke breaks up until about two hours prior to PET scans. It is very unlikely that the smoking on the morning of the scans would cause kappa receptors to upregulate. Since these individuals have been smoking and drinking regularly, we expect that any receptor regulation from smoking probably happened a long time ago. Further, if there is any acute dynorphin release associated with a smoking break, it will occur sufficiently early relative to the start of the PET scan to minimize any residual effect of transiently elevated dynorphin on our measurements of KOR level (BP_{ND}).

Recruitment:

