We will recruit heavy drinkers who consume between 20-65 drinks per week for women and 25-70 drinks per week for men. The lower limits reflect alcohol consumption that just exceeds the WHO Brief Intervention Study Group guidelines (WHO guidelines) for non-hazardous drinking, which are no more than 4 drinks/day 4-5 days per week for men (20 drinks) and no more than 3 drinks/day 5 days per week for women (15 drinks). The upper limits were chosen to ensure that we chose subjects whose typical drinking quantities would be unlikely to exceed the amount of alcohol that would be available to them for possible administration during the laboratory session. These criteria are similar to the ones being used in our ongoing work with memantine in HIC # 0602001068. We will also recruit healthy controls to match the demographics and background of the heavy drinkers, including family history of alcoholism; these controls will be light social drinkers consuming less than or equal to 20 drinks per week for women, and less than 25 drinks per week for men in the past 90 days and not meet past or current criteria DSM-IV abuse or dependence criteria for the past 5 years. The remainder of the exclusion criteria will be similar to the heavy drinkers.

Justification of Age Criteria and for Excluding Children and Adolescents Under 21 Years of Age:

We will not use subjects under 21 years of age in this study. First and foremost, this is an alcohol self-administration study in which we will be offering drinkers an opportunity to consume alcohol, and in the State of Connecticut the legal age limit for drinking alcohol is 21. Secondly, subjects below the age of 21 have probably been drinking alcohol for a shorter duration of time and will have different patterns of drinking from older drinkers, which may affect drinking during the self-administration paradigm and confound study results. The upper age limit was determined using our pilot data [3] which indicates that the majority of the subjects who participated in our ongoing study were in this age range.

Justification for choice of naltrexone dose:

We will use naltrexone in a dose of 100 mg/day. The 100 mg/day dose has shown efficacy in many recent clinical trials [9], and our own preliminary evidence suggests that this dose may produce greater reduction in drinking in FHP drinkers than the 50 mg dose.

Procedures:

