|  Flyers |  Internet/Web Postings |  Radio |
|  Posters |  Mass E-mail Solicitation |  Telephone |
|  Letter |  Departmental/Center Website |  Television |
|  Medical Record Review |  Departmental/Center Research Boards |  Newspaper |
|  Departmental/Center Newsletters |  Web-Based Clinical Trial Registries | |
|  Other (describe): |  Clinicaltrials.gov Registry (do not send materials to HIC) | |

2. Assessment of Current Health Provider Relationship for HIPAA Consideration:

Does the Investigator or any member of the research team have a direct existing clinical relationship with any potential subject?

Yes, some of the subjects If yes, describe the nature of this relationship.

No

3. **Subject Population** Provide a detailed description of the targeted involvement of human subjects for this research project.

56 healthy heavy drinkers who are not currently seeking treatment for their drinking behavior, between 21-65 years of age, family history positive or family history negative. Also, 10 healthy controls between 21-65 years of age matched on demographics including family history of alcoholism.

4. **Inclusion/Exclusion Criteria:** What are the criteria used to determine subject inclusion or exclusion? How will eligibility be determined, and by whom?

Inclusion criteria:

Ages 21-65

Able to read English at 6th grade level or higher and to complete study evaluations

Meet DSM-IV criteria for alcohol abuse or dependence (assessed using the SCID)

Family history criteria (assessed using the FHAM; see Assessment section)

Family history positive subjects: At least one first-degree relative with alcoholism as determined by the FHAM

Family history negative subjects: No first degree relative with alcoholism and no 2nd degree relative with alcoholism unless the participant cannot answer details about the 2nd degree family member's drinking consequences on the FHAM.

Average weekly alcohol consumption of standard drinks of at least 25-70 drinks for men and 20-65 drinks for women

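### Tobacco use is an uncontrolled potential confounder of P3: about half the heavy drinkers are expected to use it, and neither the control matching nor any planned P3 analysis names it

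*Combined protocol and SAP*

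**What the plan says.** The Specific Aims list P3 as a primary aim: "To determine if baseline KOR availability differs between heavy drinkers and healthy control socialdrinkers". This is a comparison between groups at a single time. Controls take no medication and do not complete the drinking sessions, and the payment schedule gives them one PET scan.

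The Research Plan, item e (Tobacco Use and Smoking breaks), reports: "In our experience, 50% of alcoholics who participate in our projects smoke cigarettes or use other tobacco products". On scan days, "we will allow regular smoke breaks up until about two hours prior to PET scans". For longer-term effects, the paragraph says of people who have been smoking and drinking regularly that "we expect that any receptor regulation from smoking probably happened a long time ago".

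Matching is described in three places. The Research Plan (recruitment text) says: "We will also recruit healthy controls to match the demographics and background of the heavy drinkers, including family history of alcoholism". Section VII, Recruitment Procedures, uses almost the same words. Section VII, Subject Population, is narrower: "10 healthy controls between 21-65 years of age matched on demographics including family history of alcoholism". None of them mentions tobacco. The exclusion criteria exempt nicotine from the substance-dependence exclusion, and controls have similar exclusions, so tobacco use is neither required nor barred in controls.

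Statistical Considerations covers P1, P2, S1 to S3 and A1. It has no entry for P3. The assessment list has no dedicated tobacco measure.

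**The concern.** The protocol's answer on smoking has two parts. The smoke-break rule deals with acute effects on the scan. The statement that any regulation is old deals with change between a person's two scans. Neither addresses a lasting difference between people who use tobacco and people who do not.

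That difference matters for P3. If tobacco use has shifted KOR availability over years, and the heavy drinkers contain more users than the controls, part of the P3 contrast reflects tobacco. Depending on its sign, this could create an apparent alcohol difference or hide a real one. As written, the plan would be satisfied by ten controls who do not use tobacco, and nothing in the analysis would show or correct the imbalance.

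**Working it through.** **Plan's own figure.** There is none for P3. The only power calculation concerns family history and does not enter here.

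**Inputs from the documents**
- Tobacco use among heavy drinkers: about 0.5 (Research Plan, item e; experience from past projects, not a target).
- Group sizes: 56 heavy drinkers and 10 controls (Targeted Enrollment; Subject Population). Recruitment Procedures says 25 controls.
- Test level: two-sided 0.05 (Statistical Considerations).

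**Inputs assumed, because the documents give neither**
- Share of controls who use tobacco, p: 0 to 0.2.
- Shift in baseline BP_ND with tobacco use, δ: 0.5 to 1.0 SD, with 0 as the null case. The SD is that within users or non-users.

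**Why the within-person comparison is protected.** Occupancy = (BP_baseline − BP_NTX) / BP_baseline. If long-term tobacco use multiplies receptor availability by a factor s at both scans, s appears in the numerator and the denominator and cancels.

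**Why P3 is not.** Let a be the true alcohol difference.
- Expected difference = a + δ × (0.5 − p), so bias = δ × (0.5 − p).
- Smallest non-null case: 0.5 × (0.5 − 0.2) = 0.15 SD.
- Largest case: 1.0 × (0.5 − 0) = 0.50 SD.
- No tobacco effect: 0.

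**Rejection rate with a = 0.** I simulated an unadjusted two-sample t-test, with each person's tobacco status drawn at the stated rate. Mixing users and non-users also widens the heavy-drinker spread: at δ = 1.0 the variance is 1 + 0.25 = 1.25.

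| Control users | δ (SD) | Bias (SD) | 56 vs 10 | 56 vs 25 |
|---|---|---|---|---|
| 0% | 0.5 | 0.25 | 10% | 17% |
| 0% | 1.0 | 0.50 | 24% | 47% |
| 20% | 0.5 | 0.15 | 7% | 9% |
| 20% | 1.0 | 0.30 | 11% | 20% |
| 50% | 0.5 or 1.0 | 0 | 5% | 5% |

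More controls make a false rejection likelier, because the same bias is measured more precisely. For scale, the smallest true difference detectable with 80% power is 0.98 SD with 10 controls and 0.68 SD with 25.

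**Chance imbalance.** Even if controls came from a population with 50% users, 10 controls would include 3 or fewer users with probability (1 + 10 + 45 + 120) / 1024 = 17%. An explicit recruitment target is therefore safer than relying on the source population.

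**Precision after allowing for tobacco** (standard error of a mean difference, in SD units)
- All 56 vs 10: √(1/56 + 1/10) = 0.34.
- Non-users only, if no control uses tobacco, 28 vs 10: √(1/28 + 1/10) = 0.37.
- Within one stratum, if controls are split evenly, 28 vs 5: √(1/28 + 1/5) = 0.49.

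**The case against.** The strongest objection is that the size is built on assumptions. The documents give no tobacco rate for controls and no effect of tobacco on KOR, and an effect of zero is possible. That stands: the documents support an unaddressed possibility, not a demonstrated bias.

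Four stronger readings are tempting and should not be drawn:

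- A reader might infer that the protocol admits that smoking alters the receptor. Its sentence is conditional: if there was any regulation, it is old. The paragraph is about whether smoking near the scan disturbs the measurement, and it says nothing about P3.
- A reader might infer that controls are matched on demographics and family history alone. Two of the three descriptions also say background, and family history is given as an inclusion, so the list is open. Tobacco could be meant. But the word is undefined, is missing from Subject Population, and is nowhere tied to tobacco.
- A reader might put the false-rejection rate at 30%, the ordinary t-test power for a 0.5 SD shift at 56 vs 10. That ignores the wider spread in a half-user group. Under the assumptions that produce 0.5 SD, the rate is 24%, and that is the extreme corner of the range.
- A reader might infer that nothing could rescue P3 if no control used tobacco. About 28 of the 56 heavy drinkers would also be non-users, so a comparison of non-users remains possible. It would have to be planned, and it says nothing directly about users.

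It can also be said that the missing P3 analysis and the conflict between 10 and 25 controls are larger gaps. They are separate matters, and writing a P3 analysis without naming tobacco would leave this one open.

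**Conclusion.** The point holds as an uncontrolled potential confounder of a primary aim, with unknown size and direction. What is firm is the logic: an argument that rests on long-standing effects cannot protect a between-group baseline comparison, and no section names tobacco as a matching factor or as a P3 covariate.

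The figures of 0.15-0.50 SD and 7-24% (9-47% with 25 controls) rest wholly on the assumed control rate and tobacco effect. They show only that the issue could matter. The documents do not support saying that P3 is biased, or in which direction. The within-person aims are not affected by this argument. The change is worth making before controls are recruited.

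**What to change.** - In the Research Plan recruitment text and in Section VII, Recruitment Procedures and Subject Population, name current tobacco use as a matching factor, with a target so that the control share is about that of the heavy drinkers (about half on the protocol's expectation). Use the same wording in all three places, and reconcile the number of controls.
- State that the existing PET-day smoking-break rule applies to controls too. Its wording may already cover them, but the supporting argument describes only people who smoke and drink regularly.
- Record tobacco use at intake in both groups.
- Add a P3 entry to Statistical Considerations that reports the group difference adjusted for, or stratified by, tobacco use.

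The cost is some wording, one baseline variable and possibly slightly slower recruitment, since light drinkers who use tobacco may be harder to find. Adjustment with about 10 controls will be imprecise, especially within strata, so the adjusted overall difference should carry the conclusion and the stratum results should be descriptive.

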Analysis of Initial Cohort: Data from the first 6 FHP and 6 FHN subjects scanned in year one of the project (24 scans total) will be analyzed to determine whether or not a reference region exists for [11C]LY2795050 ([11C]-PKAB) and whether or not the scan duration can be shortened without loss of precision of the data. To be sure that a reference tissue model is appropriate in our study, two findings are required. The V_T of the putative reference region must be unchanged by blocking and the endpoint, BP_{ND} , estimated by the reference region method must agree with the BP_{ND} calculated using an AIF. If the BP_{ND} values from 2T and SRTM continue to show excellent agreement, as applied to *both* baseline and NTX scans, then we may choose to discontinue arterial sampling thereafter and rely solely on a reference region model for analysis. After a preliminary analysis of the initial cohort, we will determine the acquisition protocol for the remaining 24 subjects.

Modeling of PET data to yield BP in regions of interest and parametric images

1. Standard kinetic modeling approaches: With plasma input function measurements in hand, we can compare multiple standard methods of estimating our desired endpoints (BP_{ND} at baseline and difference in BP_{ND} from baseline to NTX) to determine the best model or technique [52] that yields the lowest variance in the estimates. Tentatively based on preliminary data, we expect to use the cerebellum as the reference region for reference region methods but we will continue to investigate the possibility of another (better) reference region.

2. Measuring occupancy does not depend on displacement, time of day:

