Seven healthy volunteers, age = 26 ± 6 (5 males and 2 females), participated in a test-retest study of [^{11}C]LY2795050 ([C-11]-PKAB), an antagonist PET radiotracer for the KOR. Each subject received two bolus injections of up to 20 mCi of radioactivity and mass dose of $\leq 10 \mu\text{g}$ for each injection. The injected activity dose was $13.0 \pm 4.6 \text{ mCi}$, specific activity was $0.59 \pm 0.22 \text{ mCi/nmol}$ at time of injection, and injection mass was $8.8 \pm 1.2 \mu\text{g}$ across all subjects. Arterial (plasma) input function (AIF) curves were prepared from arterial samples taken during the study. Metabolite fraction was applied to yield an input curve for the native tracer only. BP_{ND} throughout the brain (calculated two different ways) was used as the study endpoint. Further details of our standard image processing methods are given below under „PET methods”.

d. Distribution of [^{11}C]LY2795050 ([C-11]-PKAB) in the brain

Figure 2 shows the early- and late-time distributions of [^{11}C]LY2795050 ([C-11]-PKAB) in the brain. The early image is an average of the 0-10 min data (middle row); it reflects initial entry into the brain via blood flow. The late image is an average of the 60-120 min data (bottom row) and reflects preferential retention of the tracer by brain regions containing specific binding sites for the tracer. Rank order of activity uptake was as follows: amygdala (AMY) > cingulate cortex (CIN) > globus pallidus (PAL) ~ putamen (PUT) > temporal cortex (TEM) ~ frontal cortex (FRO) > hippocampus (HYP) ~ caudate (CAU) > cerebellum (CER). The distribution of tracer at late time agrees with the known distribution of kappa receptors in the brain [34-36].

e. Time-activity curves: for use with kinetic models

Estimates of kinetic parameters require regional tracer concentration values over time. Automatic regions-of-interest (ROI) were applied (see PET methods) to the dynamic emission images to generate time-activity curves (TACs) in 13 ROI's. The time-activity curves (TAC) were fitted to the 4-parameter, 2-tissue compartment model (2T) using the metabolite-corrected input function. Examples of fitted TACs are shown in Figure 3. All of the regions were fit well by the 2T model. The rapid efflux from the cerebellum compared to the other regions suggests that the cerebellum has little to no specific binding and is therefore a possible reference

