region. However, the definitive identification of a reference region must be based on displacement experiments.

f. Regional distribution of desired endpoint: KOR at baseline (BP_{ND})

We computed BP_{ND} in each ROI two ways. One method requires the use of AIF and the other does not. From the fits of the TAC data via 2T model with AIF, we calculated BP_{ND} as the relative difference in volumes of distribution between the target ROI and the putative reference region, in this case, cerebellum: $(V_T(ROI) - V_T(CER)) / V_T(CER)$. BP_{ND} was also computed using the Simplified Reference Tissue Model (SRTM) using the cerebellum as the reference region. The regional distribution of BP_{ND} based on 2T and SRTM is shown in Figure 4. Figure 4 shows that the methods are in close agreement and the variability, by region, across the cohort is small.

[figure not shown]

Figure 5 **a.** Effect of pre-block with unlabeled KOR antagonist drug. Baseline TACs for cerebellum (CER), caudate (CAU), and frontal cortex (FRO) (solid circles, open circles, diamond, all in red). Curves after pre-block (blue) all show reduced specific binding and are nearly indistinguishable from CER at baseline. Curves are from one animal and are normalized to injected activity dose. **b.** BP_{ND} is reduced dose-dependently according to dose of specific KOR antagonist in both CAU and FRO region.

g. Pre-blocking of [11C]LY2795050 ([C-11]-PKAB): can we detect drug occupancy at kappa sites?

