We can verify that uptake and retention of [11C]LY2795050 ([C-11]-PKAB) is due to specific binding to KOR by looking at pre-blocking studies with well-characterized (unlabeled) drugs. Pre-blocking studies were performed in 3 rhesus monkeys. The experiments were similar to what is being proposed herein to measure occupancy of KOR by NTX. In the preliminary studies, rhesus monkeys were given iv, 1mg/kg naloxone, a non-selective KOR antagonist, or varying doses of LY2456302, a selective kappa antagonist developed by an industry partner. Example results for the blocking studies are shown in two parts of Figure 5. Figure 5a: At baseline, regions such as CAU and FRO appear to have more uptake than CER. Under pre-block with the specific KOR antagonist, TACs for two target regions (CAU and FRO) are nearly identical to the putative reference region (CER) in the unblocked case because they reflect only (the same) non-displaceable binding. The data from these two experiments on the same animal have been normalized by injected activity. The behavior of the regions shown is typical. These data are suggestive, but not definitive proof that CER is a valid reference region (See "SRTM vs. 2T", immediately below for criteria). Further evidence of specific binding in CAU and FRO is shown in 5b. BP_{ND} declines in a dose-dependent manner as the specific KOR antagonist dose is increased from low to high.

[figure not shown]
[figure not shown]

Figure 6. Percent change in BP_{ND} from test to retest scans for both 2T (blue bars) and SRTM (red bars) models. Each region is based on the average of 7 subjects. Test/retest variability is actually slightly better for SRTM estimates than for 2T.

h. SRTM vs 2T: Can we use a reference region model?

A reference region model such as SRTM has a number of practical advantages. Its use obviates the need for arterial sampling, thus decreasing the risk to the patient and simplifying the PET experiment. Figure 4 shows that estimation of BP_{ND} via SRTM and 2T is in good agreement and that use of the reference region method would be justified. In this case, CER was used as the reference region. The correlation based on all regions over all subjects was $BP_{ND}(SRTM) = 1.01 * BP_{ND}(2T)$, $R^2 = 0.98$,

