which confirms near-perfect agreement. Note: this agreement between the 2T and SRTM does not *validate* the CER as a true reference region. It indicates a valuable fact: the two estimates of BP_{ND} are consistent (they might both be biased for different reasons). For many purposes, consistency may be sufficient to argue for adoption of the SRTM or other reference method. For the reference region to be validated (i.e., shown to be devoid of specific binding), we must also show that V_T of the region does not change in the presence of a pre-blocking drug such as NTX.

- i. Percent change between „test“ and „retest“ scans: How small an effect can we detect?

Small test/retest variability is essential for us to be able to detect small differences between conditions. For each subject, the test-retest variability was measured by computing the ratio of the difference between binding potentials to their means:

$$\frac{100 * (BP_{ND}(TEST) - BP_{ND}(RETEST))}{[\frac{1}{2} (BP_{ND}(TEST) + BP_{ND}(RETEST))]}$$

The mean test-retest variability indices were 8.2% (2T) and 7.2% (SRTM) indicating that BP_{ND} values increased during the retest scan (conducted in the afternoon of the same day) compared to the test scan, across all regions. Figure 6 shows the test/retest comparison as an average value over subjects for all regions.

- j. 90 min vs 120 min results: Can we shorten the scan?

A 1 ½ hr PET scan is slightly less burdensome for the subject than a 2 hr scan and given the fairly rapid kinetics of the tracer, it seems worth considering the shorter scan. Therefore, we compared results of BP_{ND} estimates from the SRTM model using the full 120 min worth of scan data and using only 90 minutes of data. The answers were nearly identical. The correlation plot between the two families of estimates is shown in Figure 7. We conclude from this exercise that we need only to scan for 90 minutes in each scan session. A shorter scan time could improve subject compliance.

- k. BP_{ND} images

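### The agreement condition for stopping arterial sampling has no metric, level or threshold, and its only numerical precedent, a pooled R² of 0.98, does not show that 2T and SRTM agree between subjects or on occupancy

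*Combined protocol and SAP*

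**What the plan says.** **The decision.** *Analysis of Initial Cohort* (Research Plan, PET Methods) uses the first 12 heavy drinkers, six per family-history group and 24 scans in all, to decide whether a reference-region model can replace the arterial input function. V_T of the reference region must not change under blocking, and reference-model BP_ND must agree with BP_ND from arterial data. If BP_ND "values from 2T and SRTM continue to show excellent agreement", on baseline and NTX scans alike, the team may choose to stop arterial sampling. No statistic, level of analysis or cut-off is given.

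**The precedent.** The agreement that is to continue is described in Section VI, item 2.
- Subsection c: the sample is "Seven healthy volunteers, age" 26 ± 6, scanned twice for test-retest, without NTX.
- Subsection e: regions of interest were applied "to generate time-activity curves (TACs) in 13 ROI's".
- Subsection f: the two methods are said to agree closely by region, and "the variability, by region, across the cohort is small".
- Subsection h: "The correlation based on all regions over all subjects was" BP_ND(SRTM) = 1.01 × BP_ND(2T), R² = 0.98, a result "which confirms near-perfect agreement". It warns that this does not validate the cerebellum, since the two estimates may be consistent yet "they might both be biased for different reasons". It adds that consistency may be enough for many purposes.

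**The planned analysis.** Statistical Considerations, Secondary Aims 2 and 3, plans correlations between 2T and alternative models, at no stated level. It allows a simpler model if the group variance of baseline KOR is no larger than with 2T.

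**The concern.** P1, P2 and A1 use each subject's occupancy. P3 and S1 use each subject's baseline KOR. None of them compares brain regions. A correlation over all region-by-subject points includes the spread between regions, and subsection d describes a clear regional ranking from amygdala down to cerebellum. If spread between subjects within a region is small, as subsection f says, most of the variance behind a high pooled R² may come from a contrast that no aim uses.

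A team that applies the only worked example in the document could therefore satisfy the agreement condition without learning whether SRTM reproduces the subject differences on which the aims depend. Arterial data that are not collected cannot be recovered. The section counts 24 remaining subjects; with the 56 heavy drinkers in the Research Plan it would be 56 − 12 = 44.

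**Working it through.** **1. The plan's own figure.** R² = 0.98 cannot be reproduced, because the BP_ND values are only in figures that are not available here. What can be checked is what it implies.

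**2. Baseline BP_ND within a region.** Set the total variance of BP_ND over all region-by-subject points to 1. Let s be the share between subjects within regions, so that 1 − s lies between regions. A pooled R² of 0.98 leaves 0.02 as disagreement. If that disagreement varies from subject to subject,

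within-region R² ≈ 1 − 0.02/s.

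| Between-subject share s (assumed) | Calculation | Within-region R² |
|---|---|---|
| 50% | 1 − 0.02/0.50 | 0.96 |
| 20% | 1 − 0.02/0.20 | 0.90 |
| 10% | 1 − 0.02/0.10 | 0.80 |
| 5% | 1 − 0.02/0.05 | 0.60 |

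A simulation with 12 subjects and 12 target regions (13 less the cerebellum), pooled R² held at 0.98, gives similar values. With assumed regional means of 0.2 to 1.0, within-region R² is 0.77, 0.91 and 0.95 at between-subject CVs of 10, 20 and 30%. With a narrower assumed range of 0.5 to 1.0 it is 0.90, 0.96 and 0.97.

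The reported equation shows no intercept. If its R² is uncentred, it says less still: in these simulations the uncentred value was 0.996 to 0.999 where the centred value was 0.98.

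**3. Occupancy.** Occupancy is 1 − r, with r = BP_ND(NTX)/BP_ND(baseline). Assume mean BP_ND 0.5, total SD 0.25 and mean occupancy 60%, so r = 0.40. Relative disagreement per scan then has variance q² = 0.02 × 0.25²/0.5² = 0.005, an SD of about 7%. The disagreement variance in r depends on its structure:
- proportional to BP_ND, 80% shared by a subject's two scans: 2 × 0.2 × r² × q² = 0.00032
- proportional, independent between scans: 2 × r² × q² = 0.0016
- same absolute size on both scans, independent: (1 + r²) × q² = 0.0058

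R² ≈ (between-subject variance of occupancy)/(that variance + disagreement variance).

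| Structure (assumed) | Occupancy SD 5 points | 10 points | 15 points |
|---|---|---|---|
| Proportional, 80% shared | 0.89 | 0.97 | 0.99 |
| Proportional, independent | 0.61 | 0.86 | 0.93 |
| Same absolute size, independent | 0.30 | 0.63 | 0.80 |

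For occupancy averaged over regions, the simulation (proportional disagreement, independent between scans) gives 0.45 to 0.97 when 80% of the disagreement is common to a subject's regions, varying mean occupancy from 0.30 to 0.85 and its SD from 0.03 to 0.10. It gives 0.94 to 0.99 when the disagreement is independent across regions.

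**4. Do NTX scans sharpen a pooled correlation?** No. Pooling baseline and NTX scans gave R² of 0.98 to 0.995 in every setting.

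**5. Do the other conditions fill the gap?**
- The V_T condition tests whether the reference region lacks specific binding, not whether SRTM reproduces subject differences.
- Agreement on each scan condition is not agreement on the ratio of the two.
- The variance comparison covers baseline KOR only, and a model that compresses true differences between subjects would pass it.

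**The case against.** - **The plan does not name the pooled R² as its test.** A reader might infer that the initial cohort will be judged on it. The documents do not say so: the figure is preliminary, and the later correlations could be run per region. This stands, and it makes the defect an unspecified criterion with a pooled precedent.
- **Regional evidence may exist.** Figures 4 and 6 are described as regional comparisons of the two methods and are not available here. Only the text lacks within-region agreement figures. This stands.
- **There are other safeguards.** V_T must be unchanged, both scan conditions count, stopping is discretionary, and the kinetic-modelling item compares methods on the change in BP_ND. These are real, but that comparison is by variance, and none of them measures agreement between subjects or on occupancy.
- **2T is not truth.** Subsection i reports test-retest indices of 8.2% for 2T and 7.2% for SRTM, so part of any disagreement may be 2T noise. Low concordance alone would not show that SRTM ranks subjects worse. This stands and shapes the fix.
- **The low values depend on assumptions.** They do. If between-subject variance is at least 20% of the total, within-region R² is 0.90 or more. Under favourable error structures occupancy agrees very well.

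**Conclusion.** The agreement condition for stopping arterial sampling has no metric, level or threshold. Neither its only numerical precedent nor the planned correlations establish agreement on the quantities used in P1-P3, S1 and A1. With pooled R² at 0.98, within-region R² runs from 0.96 down to 0.60 as the assumed between-subject share falls from 50% to 5%. Occupancy agreement can be excellent or poor depending on an error structure that the documents do not describe.

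Three stronger readings are not supported. A reader might infer that SRTM and 2T do disagree between subjects; nothing in the text shows this. A reader might infer that all aims are exposed; S2 and S3 are methodological. A reader might infer that sampling stops automatically; the plan leaves it to the team. The change is still worth making, because the decision cannot be reversed for the subjects it affects and the check uses scans already planned.

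**What to change.** Before the 12-subject analysis, amend *Analysis of Initial Cohort* and the Secondary Aims 2 and 3 paragraph of the Statistical Considerations.

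- Replace the undefined agreement wording and the correlations with agreement across subjects within each ROI: mean difference, limits of agreement, and an intraclass or concordance coefficient.
- Report these for baseline BP_ND, NTX BP_ND and each subject's occupancy. If the aims will use a regional average, report them for that average too.
- Fix numerical thresholds in advance and give confidence intervals, since 12 subjects will estimate a coefficient imprecisely.
- Set and read the thresholds against the test-retest variability of both 2T and SRTM. The reported indices are said to reflect an afternoon rise, so systematic shift and random spread need separating first.
- Keep the V_T condition.
- State that an R² pooled over all regions is not evidence for stopping arterial sampling.

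The cost is wording and a few summaries from the 24 scans already planned. The downside is that the criterion is harder to meet, so arterial sampling may continue in more subjects.
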